8.2 Costs Analysis

Costs will be estimated as the sum of the product of resources (e.g. staff minutes) times unit costs (e.g. compensation levels). We will assess costs twice in each of the two Aim 1 trial arms: once before and once after adoption of SPIRIT, in order to compare costs of standard of care to SPIRIT. “Economic” costs (the true value of resources consumed or “opportunity cost”) will be assessed by identifying the value of subsidized or donated resources with information from data bases (e.g. wage rates) and donors, and, as needed, three price quotes from appropriate market sources. Costs for capital items (equipment) will be amortized on a straight-line basis over expected useful life, and assuming no salvage value. We will further allocate expenditures across three areas: i) medications ii) service delivery iii) indirect costs consisting of intervention overhead and administration. If possible, we will document changes in unit cost over time as programs potentially achieve greater scale, experience, and efficiency. We will also estimate the changes in HIV medical care costs due to use of changes in TB case rates. We will accomplish these calculations using projected costs for TB care.

After computing the intervention cost per participant initiating and completing IPT, we will quantify **net costs** – i.e. program costs adjusted for added or averted health care costs. We will base changes in short-term health care costs on household surveys (household expenditures for illness episode and hospitalizations). Longer-term health care costs will be projected using clinical simulation modeling, based on observed changes in health status (e.g. TB- or HIV-related morbidity), combined with estimates from the trial and published studies of the costs of managing these conditions. We will explore uncertainty in this measure with sensitivity analyses.

8.3 Health Effects

Health effects will be quantified in two ways. First, we will use directly measured study outcomes pertaining to health-related events (TB cases, deaths, hospitalizations). Second, we will integrate the health impact of averted TB cases using **disability-adjusted life years (DALYs)**, including lost years of life and the collective disability effects of adverse events. DALY estimates will be for the short term (during the trial) and the long term (5, 10, and 20 years) using clinical modeling. We will estimate future changes in DALYs among infected individuals by projection duration of survival and morbidity given best estimates of projected IPT initiation rates and use of ART. We will conduct extensive sensitivity analysis on our assumptions, to describe the range of probable DALYs averted. We will also calculate the DALYs averted due to each TB infection averted due to IPT, using data from our own ongoing studies and published estimates of TB transmission rates.

8.4 Cost-effectiveness Analysis

We will calculate efficiency (CE) indicators, such as program cost per person starting IPT, per person completing IPT and per TB case averted. We will calculate the standard CE ratio, net cost per DALY averted, with net costs equal to program costs adjusted for changes in health care costs due to the intervention. We will calculate this ratio with and without the projected long-term effects. All future costs and health effects will be discounted at 3% per year, per standard practice. We will conduct extensive univariate and multivariate sensitivity analysis. Importantly, if the intervention yields net savings (i.e., negative net costs) as well as health benefits, the intervention is classified as “dominant” and no CE ratio is calculated.

9. SPIRIT Enhanced Business Training & “Training-of-trainers” curriculum

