8.1 Costs

We will use standard micro-costing techniques to measure the cost of each component of the SPIRIT intervention. This will include costing of training activities and efforts made to transfer knowledge to DHOs in meetings; costs associated with utilizing opinion leaders to teach DHOs; costs of the SPC for administering INH, SMS system development and implementation, and other communication efforts; and costs of biannual meetings held with DHOs. This costing process will quantify the resource and associated unit costs required to deliver each intervention step, organized in standard expenditure categories—personnel, supplies, equipment, services (e.g. electricity), space, and overhead. Costs will be allocated to each intervention step to the extent possible and review of the division of shared resources and staff time, noting and reporting uncertainties in these divisions. Information required to determine costs will be obtained through examination of expenditure records, discussion with program managers and staff including pharmacy, care delivery labs and observation of service delivery for a sample of patients. Focused “time and motion” studies to allocate staff time across tasks within and outside the intervention will also be carried out to properly account for health care workers’ time devoted to the intervention. Donated and subsidized resources will be appraised at market value. We will assess costs from the societal perspective, i.e. including costs to patients and their family members in the form of out-of-pocket expenditures and also lost productivity. To assess costs incurred by patients, we will administer short questionnaires to patients selected for participation in the Aim 2 sub-sample at intervention and control facilities that elicit their expenditures for transportation to receive treatment and the value of the time lost in accessing care by clients and accompanying family members and time lost due to illness.

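### Protocol 8.1 sets a societal perspective, but the net-cost formula in 8.2 and 8.4 has no explicit term for patient and family travel, access time or lost productivity

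*Protocol*

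**What the plan says.** Protocol 8.1 states the perspective: "We will assess costs from the societal perspective, i.e. including costs to patients and their family members in the form of out-of-pocket expenditures", and adds lost productivity. It plans short questionnaires in the Aim 2 sub-sample covering transport spending and "the value of the time lost in accessing care by clients and accompanying family members and time lost due to illness".

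Protocol 8.2 defines net cost as "program costs adjusted for added or averted health care costs". It gives a source for part of the second term: "We will base changes in short-term health care costs on household surveys (household expenditures for illness episode and hospitalizations". It also sorts expenditure into three areas, "i) medications ii) service delivery iii) indirect costs consisting of intervention overhead and administration".

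Protocol 8.4 makes the main ratio net cost per DALY averted, "with net costs equal to program costs adjusted for changes in health care costs due to the intervention". If net cost is negative and health improves, the intervention is called dominant and no ratio is reported.

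On capital, 8.2 equates economic cost with opportunity cost, then says: "Costs for capital items (equipment) will be amortized on a straight-line basis over expected useful life, and assuming no salvage value". Section 8.4 says: "All future costs and health effects will be discounted at 3% per year".

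SAP section 1 says that the analysis plan for cost-effectiveness outcomes is held elsewhere.

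**The concern.** The stated perspective is wider than the stated formula. An analyst who follows 8.2 and 8.4 literally would collect patient travel and time costs under 8.1 and then have no line in the numerator on which to enter them. An analyst who starts from 8.1 would add them. Both could claim to follow the protocol, and the choice could be made after the results are known.

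This matters for SPIRIT because several options that the toolkit in 5.3.2 may include, such as 90-day supply, pharmacy-only visits and community adherence groups, change how often or how long patients attend. In the other direction, IPT courses that would not otherwise have happened may add visits. Both effects fall partly on patients and families, and the dominance rule turns on the sign of the same net cost.

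The equipment rule raises a smaller question of the same kind. A straight-line charge recovers the purchase price but puts no cost on the money tied up, which an opportunity-cost definition implies.

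**Working it through.** The plan states no cost, ratio or equipment figure, so there is nothing to reproduce. The check compares the sections and then sizes what can be sized.

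**1. Which costs reach the numerator.** Let P be program cost, ΔH the change in health care cost, and ΔF the change in patient and family cost that is not already in ΔH.

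- As written in 8.2 and 8.4: N = P + ΔH.
- As implied by 8.1: N = P + ΔH + ΔF.

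Item by item, for the patient and family costs in 8.1:

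- Household spending on illness episodes and hospitalizations enters, through ΔH (8.2).
- Transport to receive care has no explicit term.
- Time lost accessing care, by patients and accompanying family, has no explicit term.
- Lost productivity has no explicit term.
- Time lost to illness has no explicit term in N, but 8.3 counts disability in DALYs, so adding it to cost could count it twice.

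**2. Effect on dominance.** The two versions of N give opposite dominance calls when ΔF has the opposite sign to P + ΔH and is larger in absolute value. Nothing in the documents says whether this is likely.

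**3. Possible sign of ΔF.** Protocol 6.2 gives 5 refill visits under monthly prescribing and defines completion as 180 pills. Monthly supply means 180/30 = 6 dispensings, or 5 refills after the first. A 90-day supply means 180/90 = 2 dispensings, or 1 refill. With an unknown patient cost c per visit:

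- Changing from monthly to 90-day supply saves (5 − 1)c = 4c.
- A monthly course that would not otherwise have occurred costs 5c.
- If every refill coincides with an ART visit, the amount is about 0.

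The documents give no value for c and no mix of these cases, so neither size nor direction can be stated.

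**4. Equipment.** Inputs are r = 3% (8.4) and no salvage value (8.2). Useful life L and the equipment share s of total cost are my assumptions. The straight-line annual charge per unit of price is 1/L. The annuity charge is r/(1 − (1 + r)^−L). The rise in total cost is s × (annuity ÷ straight-line − 1).

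| L (years) | Straight-line | Annuity at 3% | Ratio | Total, s = 5% | Total, s = 20% |
|---|---|---|---|---|---|
| 3 | 0.3333 | 0.3535 | 1.061 | +0.3% | +1.2% |
| 5 | 0.2000 | 0.2184 | 1.092 | +0.5% | +1.8% |
| 10 | 0.1000 | 0.1172 | 1.172 | +0.9% | +3.4% |
| 20 | 0.0500 | 0.0672 | 1.344 | +1.7% | +6.9% |

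The activities costed in 8.1 are mainly training, opinion leaders, medication, SMS and meetings, and equipment is one of six expenditure categories. The left-hand share is therefore the more plausible one, but no share is given.

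**The case against.** The strongest reply is that the text is ambiguous and does not state an exclusion. Section 8.1 sets the societal perspective for costs in general, and program cost is nowhere defined so as to shut out the patient costs just promised. Some household spending demonstrably enters through the health care term. A reader might therefore infer too much in saying that all patient and family costs are left out; the household-survey sentence in 8.2 contradicts that. The three-area list is no proof either, since it is a breakdown of expenditure and does not define the numerator. Nor does 8.4 itself attach a societal label to its ratio.

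These points stand, but they do not close the gap. The household-survey sentence covers spending on illness and hospital stays, not travel and time for IPT visits. Elsewhere (Aim 4 in section 2, and the efficiency indicators in 8.4) program cost is used for cost per initiation, completion and TB case averted, which reads more naturally as the cost of delivering the intervention.

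It is also fair to say that section 1.2 describes IPT as inserted into existing ART care, which would make extra visits fewer, and that the toolkit options are possibilities only. That limits what can be claimed about size. The sensitivity analyses planned in 8.2 and 8.4 name neither perspective nor capital charge. The separate cost-effectiveness plan may settle both matters; its content is unknown here.

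On equipment, a reader might infer that the whole ratio fails as an economic cost. The documents do not support that: donated and subsidized resources are valued at market prices, and only the capital component lacks an opportunity cost.

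**Conclusion.** The point holds as a mismatch that needs reconciling. The perspective in 8.1 includes patient and family travel, access time and lost productivity, and the formula in 8.2 and 8.4, which also drives the dominance rule, gives them no explicit term. Its size and sign cannot be derived from the documents, so no claim that the ratio is biased in a particular direction is justified.

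The equipment rule is a real but minor inconsistency. The annual equipment charge is too low by a factor of 1.06 to 1.17 for lives of 3 to 10 years at 3%. With assumed equipment shares of 5% to 20%, that is 0.3% to 3.4% of total cost, probably near the lower end.

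Both points concern Aim 4 only. They touch no effectiveness estimate or test. The conclusion rests on the protocol text alone and could be met by the separate plan if that plan already defines the numerator and capital charge.

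**What to change.** - In 8.2 and 8.4, define societal net cost as program cost + change in health care cost + change in patient and family cost (transport, access time, productivity).
- Add counting rules. Household illness spending is counted once, illness time already reflected in DALYs is not added to cost, and each lost hour is valued once.
- Report the health-system ratio (without the patient and family term) beside the societal one, and state in advance which of them governs dominance.
- Add a fallback: if patient costs are not obtained, label the ratio as health-system perspective. This is a live risk. Section 8.1 relies on questionnaires in the Aim 2 sub-sample, but 6.1 and 11.2.2 describe Aim 2 data collection as de-identified record review, and 11.2.1 lists no patient consent. The sub-sample variables in SAP section 5 include no cost items, although that SAP covers health outcomes only.
- Annuitize equipment at the 3% rate in 8.4 over its useful life. If straight-line figures are kept, report them as financial cost.
- Align the separate cost-effectiveness plan with these definitions.

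The cost is a few sentences in 8.2 and 8.4 and one more column in the cost model. No data are needed beyond what 8.1 already promises. The societal ratio may turn out more or less favourable than the present formula would give.

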9.1. Objective

Objective: To evaluate the effect of enhanced business training among intervention group DHOs from Phase 1 (Years 1-3 of trial follow-up) in the southwestern Uganda region on IPT initiation during years 4-5 of trial follow-up (Phase 2). We propose to extend the SEARCH-IPT study for two additional years which will occur during Years 4 and 5 post trial baseline enrollment (Phase 2).

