5.2 Randomization

The SPIRIT trial investigators will form up to 14 groups of 4-7 DHOs (Figure 1). When possible, groups will be formed based on geographic, socio-demographic, and health systems characteristics. The groups will be pair-matched on geographical, socio-demographic and health systems characteristics to improve statistical efficiency. For both the creation of the groups and construction of matched pairs, geographic proximity will be optimized to facilitate DHO mini-collaboratives in the SPIRIT intervention and minimize contamination between arms. Randomization will be performed using a random number generator in standard statistical software, and overseen by the study statistician. One group in each of the 7 matched pairs will be randomized to the intervention, and one to the control condition.

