9.2. Eligibility criteria

9.2.1. Inclusion criteria

- (a) District Health Officer or District TB Supervisor (or other DHO-appointed TB focal person) from the Phase 1 Southwestern Uganda region which includes 2 intervention and 2 control DHO groups (of 5-10 DHOs/group)
- (b) By definition, the DHO and District TB Supervisors in Uganda are all ≥ 18 years of age

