9.3. Enhanced Business Training

Building on business training introduced within the SPIRIT intervention, we will provide additional management training (using a technique referred to as “Gap Analysis”⁴⁸) to a subset of SPIRIT intervention DHO groups, in the southwestern Uganda region, in order to evaluate the impact of enhanced business training on ongoing IPT initiation at quarterly meetings.

9.4. “Training-of-trainers” curriculum intervention

The “Training-of-trainers” (ToT) curriculum will include materials to support business training including slides and information materials that cover leadership and management skills taught to SPIRIT intervention-group DHOs over the first 3 years (Phase 1) of teaching mini-collaboratives. The ToT program will be designed such that intervention DHOs will provide business management and leadership training quarterly to their respective District Health Teams (DHT).

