9.5. Outcomes

The outcomes for this study aim will include changes in IPT initiation rates in Phase 2 intervention vs. control districts (see section 5.6.), and fidelity to implementation of the ToT program as defined by completion of trainings covering the full ToT curriculum.

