9.6.2. Analysis

The statistical analyses of IPT uptake will use the same methods as described for Phase 1 (see Section 5.7), limited to the SPIRIT trial intervention and control districts from the Southwestern region of Uganda. However, the outcome will be evaluated by district, rather than the pair-matched DHO groups evaluated in Phase 1.

10. “Training-of-trainers” curriculum impact on district-level management and health outcomes

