to patients who are stable in care), we will conduct two sensitivity analyses. In the first, we will assume that 97.5% of persons who previously started IPT remain in active care at the same clinic from quarter-to-quarter. In the second, we will assume that 0% of persons who previously started IPT remain in active care from quarter-to-quarter. The second sensitivity analysis is expected to be extremely conservative and will provide a lower bound in the estimated incidence rates. Altogether, PT for each clinic-quarter will be calculated as the quarter-specific number in active HIV care minus half the IPT starts in that quarter and X% of the previous IPT starts, where X% = 100% in the primary analysis, 97.5% in the first sensitivity analysis, and 0% in the second sensitivity analysis. The resulting incidences rates will be converted from being in ‘clinic-quarters’ to ‘person-years’ for ease of interpretation.

In a secondary analysis, we will calculate the two-year, cumulative incidence of IPT initiation as the total number of IPT starts, divided by the average active care size over follow-up. As before, we will calculate the district-level cumulative incidence in two ways: (1) the total starts in a district (summed over the 2 clinics) divided by the total active care size for that district (again summed over the 2 clinics); and (2) by averaging the clinic-specific cumulative incidences within each district. We will also report total starts by arm.

All analyses will assume that all adults in active HIV care are eligible for IPT at the beginning of follow-up (Q1-2019 in the Southwest and Q2-2019 in the East/East-Central). By randomization, the number in active HIV care and the number who had previously started IPT should be balanced between arms.

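### Aim 5 is worded as the effect of enhanced business training, but comparing the original Southwest arms in Phase 2 can only estimate SPIRIT and all Phase 2 additions together

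*Protocol*

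**What the plan says.** **Objective.** Protocol 9.1 gives the purpose as "To evaluate the effect of enhanced business training among intervention group DHOs from Phase 1" in the Southwest, with IPT initiation in years 4-5 as the outcome. Aim 5 in Section 2 and the synopsis in 1.1 say the same in substance.

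**Who is trained.** Section 9.3 gives the training to "a subset of SPIRIT intervention DHO groups, in the southwestern Uganda region, in order to evaluate the impact of enhanced business training". Section 9.2.1 lists two intervention and two control groups in that region.

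**What else they receive.** These groups have had three years of collaboratives, with business training already included (5.3.1, 7.1). During Phase 2 the intervention DHOs also run quarterly training-of-trainers sessions for their District Health Teams (9.4). Control DHOs receive the IPT guidelines and otherwise follow country standard (5.4).

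**Randomisation.** Section 5.2 is the only description: "One group in each of the 7 matched pairs will be randomized to the intervention, and one to the control condition". None is described for Phase 2.

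**Outcome and analysis.** Section 9.5 names "changes in IPT initiation rates in Phase 2 intervention vs. control districts". Section 9.6.2 says "The statistical analyses of IPT uptake will use the same methods as described for Phase 1", "limited to the SPIRIT trial intervention and control districts from the Southwestern region of Uganda", evaluated by district.

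**Prior starts.** Protocol 5.6.1 and 5.7, to which Phase 2 cross-refers, take earlier INH starts into account in the person-time at risk. The SAP, which covers Phase 1 only, says in its section 2: "All analyses will assume that all adults in active HIV care are eligible for IPT at the beginning of follow-up". It defends this by expecting randomisation to balance earlier starts between arms.

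**The concern.** Every DHO who gets the enhanced training has already had the Phase 1 package, and no comparison DHO has. SPIRIT groups without enhanced training exist in the East and East-Central regions, but Phase 2 is confined to the Southwest, so they are not comparators. Any Phase 2 difference mixes three things: what persists from SPIRIT, the enhanced training, and the training-of-trainers. The Protocol mentions neither carry-over nor a washout.

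There is also a gap in the person-time rule. If SPIRIT worked, fewer patients remain unstarted in the intervention arm when Phase 2 opens. Whether Phase 1 starters are taken out of Phase 2 person-time then affects the ratio, and the Protocol does not state this for Phase 2.

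At stake is whether a training programme is credited with, or denied, an effect that the trial cannot estimate. The Phase 1 primary result is not touched.

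**Working it through.** **Inputs.** The documents give no effect size or power for Aim 5, so the illustration borrows the Phase 1 planning values in SAP 6.3: 22 per 100 person-years under control, an absolute increase of 10, k = 0.25, about 21,500 person-years per group, 7 groups per arm, one-sided 5%.

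**Step 1: reproduce the plan's figure, to confirm that it means 22 versus 32.** Groups per arm for an unmatched cluster trial with rates:

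c = 1 + (z_α + z_β)² × [(λ0 + λ1)/y + k²(λ0² + λ1²)] / (λ1 − λ0)²

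The bracket is 0.54/21,500 + 0.0625 × (0.0484 + 0.1024) = 0.00945. Then c = 1 + (1.645 + 0.842)² × 0.00945/0.01 = 6.84, so 7 per arm, with power 80.9%. The plan's figure is reproduced.

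**Step 2: assumptions for Phase 2.** These are not document figures:
- a closed cohort;
- constant Phase 1 rates of 0.22 and 0.32 per person-year for 2 years (the measured window) or 3 years (the whole intervention period);
- no effect of enhanced training or training-of-trainers;
- a share f of the SPIRIT rate difference persists, so the Phase 2 rates are 0.22 in control and a = 0.22 + 0.10f in intervention.

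**Step 3: share not yet started when Phase 2 opens.**
- After 2 years: control exp(−0.44) = 0.644; intervention exp(−0.64) = 0.527.
- After 3 years: control exp(−0.66) = 0.517; intervention exp(−0.96) = 0.383.

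**Step 4: Phase 1 starters removed from person-time.** The ratio is (0.22 + 0.10f)/0.22, which gives 1.00, 1.23 and 1.45 for f = 0, 0.5 and 1.

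**Step 5: SAP eligibility assumption restarted at Phase 2 baseline.** For an arm with unstarted share S and rate a, starts in quarter q (0 to 7) are n_q = S[exp(−aq/4) − exp(−a(q+1)/4)]. Person-years are (1 − n_q/2 − earlier Phase 2 starts)/4, as in the SAP formula. Eight-quarter totals per patient in care:
- After 2 years: control 0.2293/1.7543 = 0.1307. Intervention 0.1877/1.7988 = 0.1043 (f = 0) or 0.2493/1.7248 = 0.1445 (f = 1).
- After 3 years: control 0.1840/1.8028 = 0.1021. Intervention 0.1363/1.8539 = 0.0735 (f = 0) or 0.1810/1.8001 = 0.1005 (f = 1).

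| Carry-over f | Starters removed | Restarted, 2 years | Restarted, 3 years |
|---|---|---|---|
| 0 | 1.00 | 0.80 | 0.72 |
| 0.5 | 1.23 | 0.96 | 0.86 |
| 1 | 1.45 | 1.11 | 0.985 |

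**Step 6: a change from Phase 1.** With starters removed, the Phase 2 ratio divided by the Phase 1 ratio of 1.45 is 0.69, 0.84 and 1.00 for f = 0, 0.5 and 1. Only full persistence gives the null value when the additions do nothing.

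**Step 7: what correct person-time cannot remove.** If patients differ in their propensity to start (assumed gamma frailty variance 0.5 to 1), removing starters still leaves 0.86-0.93 at f = 0 and 1.20-1.31 at f = 1. Aggregate counts cannot correct for that change in mix.

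**The case against.** **The arms are still randomised.** This is true, and it supports an effect of the whole sequence of interventions against standard of care. It does not support an effect of the one component named in the objective.

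**The outcome is a change in initiation.** Sections 9.4.1 and 9.5 do use that word, and a contrast of changes would address carry-over in part. It isolates the Phase 2 additions only if the SPIRIT effect would otherwise have stayed constant (step 6). Neither that assumption nor a change model is written, and training-of-trainers would remain mixed in.

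**Prior starts are already handled.** This largely stands. A reader might infer that Phase 2 will count Phase 1 starters as at risk again, or that a depleted pool can never be separated from the training effect. The documents do not support either inference. Phase 2 cross-refers to Protocol 5.6.1 and 5.7, which account for prior starts; the eligibility assumption is Phase 1 SAP text tied to 2019 quarters. The number of earlier starters can be removed with data already held. What is missing is a sentence saying that Phase 1 starts count as prior starts in Phase 2. The SAP's appeal to balance by randomisation cannot stand in for it after three years of different treatment.

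**A separate plan may exist.** The SAP says that business outcomes are covered elsewhere. No analysis plan can supply a SPIRIT-exposed comparator that the design does not follow.

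**The extension is openly built on SPIRIT and is not the primary aim.** Both are fair, and they limit the weight of the point.

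**Conclusion.** The point holds as a mismatch between the stated question and what is estimated. Aim 5 can estimate the combined effect of Phase 1 SPIRIT, enhanced training and training-of-trainers against standard of care. It cannot estimate the effect of enhanced training alone.

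With no effect of either Phase 2 component, the ratio could lie between 1.00 and 1.45 with starters removed. It could lie between 0.72-0.80 and 0.985-1.11 if eligibility were restarted. The two columns describe different rules and should not be combined: under a restart with full carry-over the two-year figure is 1.11, not 1.45. Carry-over and depletion act in opposite directions, so the sign of the net distortion is unknown.

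These figures rest on a closed cohort, constant rates, assumed carry-over shares, and planning rates that are trial-wide rather than specific to the Southwest. They show the scale and do not predict a result. The identification problem itself depends on none of them. The person-time limb is an unstated rule, not a demonstrated error.

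**What to change.** 1. In Section 2 (Aim 5), 1.1 and 9.1, restate the target as the combined effect of Phase 1 SPIRIT plus the Phase 2 components, enhanced training and training-of-trainers, against standard of care. Drop any claim about enhanced training alone.
2. In 9.6.2, state that cumulative Phase 1 starts enter Phase 2 person-time as previous starts, and that the SAP assumption of universal eligibility is not reused at Phase 2 baseline.
3. Report the Phase 1 and Phase 2 rate ratios side by side for the same Southwest districts, as a descriptive supplement. Do not adjust the main Aim 5 estimate for a district's Phase 1 rate: that rate arises after randomisation, lies on the path from SPIRIT, and would remove part of the combined effect in item 1.

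The cost is wording changes and use of data already held. The conclusion of Aim 5 becomes narrower.
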